#### **Enrollment**

The person or legal representative who wishes to volunteer to participate in the research shall, before commencing the research, be informed by the research team in a sufficient and comprehensible manner of the purpose, methodology, expected benefits, predictable risks, difficulties, aspects not appropriate to the health and personal characteristics of the person, and the conditions under which the research will be carried out, to be continued, and of the right to withdraw from the research at the time requested.

The study will involve 36 healthy volunteers who have natural dentition and do not have tooth deficiencies. The volunteers' participation in the study will not exceed a total of 25 minutes for two separate sessions, and no follow-up will be implemented. Volunteers may withdraw from the research during the conduct of the research without giving any reason, but they must inform the researchers in advance that they will be withdrawing from the study so as not to put them in difficulty. Data from volunteers who withdraw from the study during or after the recording session will be deleted and not included in the study. The same number of new volunteers will be included in the post-examination research conducted by relevant researchers. All healthy volunteers have been assured that, in the event of any health problems that may arise, whether directly or indirectly, as a result of the implementation of the research, any kind of medical intervention will be provided, and they will not be subjected to any financial burden related to medical interventions. In the event of severe nausea, anxiety, restlessness, or anxiousness during the surface scan and contact point recording, the investigation will be terminated for the volunteer concerned when it is indicated that the operation will be suspended or cannot be continued until it is decided to voluntarily resume.

### **Inclusion criteria**

- Voluntary acceptance of participation in the study after reading the informed and voluntary approval form
- Individuals over 18 years of age with natural dentition and without tooth deficiency
- Individuals with Angle-Class I skeletal relationships
- Individuals with no interocclusal closure problem for any reason

# **Exclusion criteria**

- Refusal to voluntarily participate in the study after reading the voluntary approval form
- Individuals with dental deficiency or restoration that may affect the closure of the foreheads
- Individuals with skeletal contact in Angle Classes II and III
- Temporomandibular joint dysfunction, pain in the orophatic region, and acute oral disease
- Individuals carrying a cardiac battery and a defibrillator
- Individuals with neck muscle problems, neck vertebrae, or benign paroxysmal positional vertigo disease/headache

# Sample size and strength analysis

This study uses the PS Version 3.0 package. =0,50,  $\alpha$ =0,05, test strength 1-=080, repetition correlation r=0,20 is the default, and the total sample size is determined to be at least 36. But because working with a larger sample reduces the level of misunderstanding, it is desirable to work with as many patients as possible.

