There are not enough studies in the literature to clinically evaluate the changes in occlusal contact points according to different head positions using digital methods. This study aims to quantitatively evaluate the changes in occlusal contact points with digital interocclusal and facebow recordings taken in three different head positions. The hypothesis of the study is that there is no statistically significant difference in interocclusal contact points in different head postures.

Research will be supported by the Scientific Research Projects Coordination Unit of the University of Hacettepe, and an agreement will be reached with the Faculty of Dental Medicine of the Hacetepe University (Hacettepe University Dental Faculty [name]), the research center, in order to reach a positive conclusion about the necessary board decisions. Support address: University of Hacettepe [name].

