#### **Statistical Evaluation**

Data from all volunteers participating in the study will be included in the statistical analysis. First, the Kolmogorov Smirnov adaptation test and the Shapiro-Wilk test are considered to be used to see if the data has a normal distribution. Subsequently, the differences between groups will be assessed using parametric or non-parametric statistical methods, depending on the case. Previous studies will be studied in detail, and comparisons will be evaluated using appropriate tests. Taking into account previous studies, it is envisaged that independent and dependent group tests, Kruskal Wallis, or one-way variance analysis, will be used.

Any possible change in the clinical research plan or process will be promptly notified to the research center, relevant institutions, boards, and healthy volunteers. Derogations from the clinical research plan are monitored and managed by the research center, and inconsistencies with the plan are expressly prohibited.

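### Do a target of 36 volunteers and an open-ended minimum of 36 leave the trial without a defined sample size?

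*Combined protocol and SAP*

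**What the plan says.** The combined protocol and SAP deals with the number of participants in two places.

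- **Enrollment:** "The study will involve 36 healthy volunteers who have natural dentition and do not have tooth deficiencies". On withdrawals it adds: "Data from volunteers who withdraw from the study during or after the recording session will be deleted and not included in the study". These people are then replaced: "The same number of new volunteers will be included".
- **Sample size and strength analysis:** the calculation (alpha 0.05, power 0.80, correlation between repeated records 0.20, and an effect of 0.50 whose symbol is lost in the text) gives 36 as the smallest acceptable total. The section then says that "it is desirable to work with as many patients as possible".

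No section sets a maximum, a closing date or an interim analysis. The Statistical Evaluation section ends with a general statement on conduct, that "inconsistencies with the plan are expressly prohibited". The hypothesis under Importance of the study is that "there is no statistically significant difference in interocclusal contact points in different head postures", with no margin.

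**The concern.** Put side by side, one section seems to fix the total at 36 and the other seems to leave it open. On a strict reading, a 37th complete participant is welcome under the sample size section, departs from the Enrollment section, and is then barred by the rule against inconsistencies with the plan.

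Two consequences would follow if the total really were undefined. First, the difference that the study can detect would not be set. Because the hypothesis is worded in terms of significance alone, the chance of rejecting it for a given small difference would depend on how many people happened to be recruited. Second, in an unblinded, single-operator study with no closing point, recruitment could in principle be extended after a look at the results, which raises the false-positive rate.

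**Working it through.** **1. Do the sections conflict?**

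| Question | Enrollment | Sample size and strength analysis |
|---|---|---|
| Figure given | 36 | 36 |
| Form | number to be recruited | minimum from a power calculation, plus a preference for more |
| Is it met by 36 complete participants? | yes | yes |

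A power calculation always returns a minimum, so the wording there is ordinary. The sentence about recruiting more states a wish and sets no second target. One-for-one replacement stops the analysed number from falling below 36, and that serves a minimum as well as a fixed total. The sample size section is part of the same plan that the conduct statement protects, so a 37th participant, whom that section expressly welcomes, is not an inconsistency with the plan.

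**2. The plan's own figure.** Whether 36 can be reproduced depends on what 0.50 measures, and the lost symbol cannot be counted against the plan. With a two-sided paired t-test:
- 0.50 SD of the within-person difference needs 34 participants, and power at 36 is 0.83;
- 0.50 SD of a single position with r = 0.20 needs 53, and power at 36 is 0.64.

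This is a separate question. It does not bear on whether the two sections agree.

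**3. What a larger number does to precision and power.** Inputs from the plan are alpha 0.05 (two-sided assumed), power 0.80 and r = 0.20. The totals of 60 and 100 and the true difference of 0.30 SD are assumptions. All results are in units of the SD of one position.

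- SD of a paired difference = sqrt(2 × (1 − 0.20)) = sqrt(1.6) = 1.265.
- 95% half-width = t(0.975, N − 1) × 1.265 / sqrt(N). At N = 36: 2.030 × 1.265 / 6 = 0.43. At N = 60: 2.001 × 1.265 / 7.746 = 0.33.
- Detectable difference and power come from the noncentral t distribution.

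| N | Detectable difference at 80% power | Power for 0.30 SD |
|---|---|---|
| 36 | 0.61 | 28% |
| 60 | 0.47 | 44% |
| 100 | 0.36 | 65% |

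Every change is in the study's favour: smaller detectable differences, more power and narrower intervals.

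**4. Type I error with one analysis.** In 20,000 simulated null trials (three positions, normal data, r = 0.20), rejection rates at N = 36 and N = 60 were:
- repeated-measures ANOVA: 4.9% and 4.9%;
- Friedman: 5.3% and 5.0%;
- one-way ANOVA: 2.3% and 2.3%;
- Kruskal-Wallis: 2.4% and 2.4%.

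The simulation standard error near 5% is sqrt(0.05 × 0.95 / 20,000) = 0.15 percentage points. No test is materially above 5%, and moving from 36 to 60 does not raise the rate.

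**The case for a change.** The best argument for a change is that nothing forbids looking and then recruiting more. The study is unblinded, one operator takes all the records, and the choice of test is left open. If the data were analysed at 36, 48 and 60 and any significant result were accepted, repeated-measures ANOVA would reject a true null hypothesis in about 9% of studies. With looks every 6 participants up to 72, the figure is about 12%. One-way ANOVA, which ignores the pairing and is conservative here, would stay between about 5% and 6.5%.

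The arithmetic is right, but the look schedules are invented for the purpose. The document describes no interim analysis, and its only stated reason for exceeding 36 is the general benefit of a larger sample. The same risk exists in any study that does not expressly rule out unplanned looks, and it does not come from calling 36 a minimum.

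The point about the hypothesis is also fair as far as it goes: with no margin, a trivial difference becomes significant once enough people are studied. That comes from the wording of the hypothesis, and capping recruitment would not cure it. What stands is that the text does not say when recruitment ends.

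**Conclusion.** The concern does not call for a change. The two sections agree on 36, and the remaining looseness is an unstated closing point that a study team would ordinarily settle by recruiting to 36 complete data sets, or somewhat more, and analysing once. Followed that way, the plan holds type I error at or below about 5% (2.3% to 5.3% across the four tests simulated), and a larger sample only improves precision, for example from a half-width of 0.43 SD at 36 to 0.33 SD at 60.

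This rests on two assumptions: that the head positions are compared once, and that the final number is not chosen in the light of results. Nothing in the document contradicts either. A line naming the number of complete data sets at which recruitment closes would be good housekeeping, but it would not alter the design, the analysis or the interpretation.

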#### **Randomization:**

The study was planned as a clinical trial. The planned digital interocclusional recordings for three different head positions will be completed in a single session, and the recording groups will not change. The total of three different records to be taken will not be subject to randomization in itself.

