## Clinical Research Plan

# Importance of the study

Head posture varies according to the physiologic and functional activity of the individual. Head postures are divided into 'active feeding position', 'head up position', and 'extended head position'. (1,2) The position in which the head extends 30° forward during feeding is known as the 'active feeding position'. (2) This posture causes the mandible and mandibular closure pathways to be positioned more anteriorly than normal. During drinking, the head extends 45° backwards and the mandible moves posteriorly. (3) Any change in head posture causes the muscles attached to the mandible to stretch and lengthen, resulting in a change in mandibular position. Changes in mandibular position result in changes in occlusal contact points and the occlusal forces generated at these points. The literature supports the relationship between head posture and occlusal contact points. (4,5)

Micron-sized changes in occlusal contacts can trigger severe dysfunction and pain in the temporomandibular joint (TMJ). Therefore, it is important to obtain accurate interocclusal records and to detect occlusal interferences. The interocclusal record is defined as a record of the positional relationships of opposing teeth and jaws. (6) Interocclusal records facilitate the assessment of occlusion for diagnostic or treatment planning purposes. Restorations with occlusal incompatibility produced using inaccurate interocclusal records result in increased adjustment time of the restoration or the need for restoration replacement. This is time-consuming and costly for both the clinician and the patient. Therefore, reliable interocclusal records obtained by providing appropriate occlusal records directly affect the success of prosthetic or indirect restorative procedures. (7)

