
# **Digital Interocclusal Record Groups**

Group 1 (G1): Digital interocclusal recording taken in the neutral position with the head aligned in the head-neck-spine plane

Group 2 (G2): Digital interocclusal recording taken in the position where the head is positioned at 30° flexion relative to the head-neck-spine plane

Group 3 (G3): Digital interocclusal recording with the head positioned in 45° extension relative to the head-neck-spine plane

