## oJMA Record

For each participant, the spatial position of the maxilla relative to the skull base, the condyle distance and the static and dynamic recording of the mandible will be taken in accordance with the digital occlusal analysis module in the oJMA.

All records will be completed in two sessions and carried out by a single operator. During the first session, participants will be scanned using the intraoral scanner (TRIOS4; 3Shape A/S; Copenhagen, Denmark) in accordance with the scanning protocol recommended by the manufacturer. Each of the scans will take 1.5 minutes and will be completed in a total of three minutes. A goniometer (Goniometer, 360°; Saehan, Germany) will be used to standardize the head position of participants before taking interocclusal records in the dental unit. (13,14) All participants will be in the dental unit, where the back of the unit will support the person's lumbar and thoracic vertebrae, with their arms freely sitting next to the body and watching directly in front of them. The neutral position of the head (G1, PN), 30° flexion (G2, PF), and 45° extension (G3, PB) will be determined by a goniometer. For each participant, the neutral position will first be determined, with the head, neck, and spine on the same axis, the fixed arm of the gonyometer standing on the ground, the central meatus acusticus externus, and the measuring arm aligned with the Camper plane. Then, for

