each head position, the measuring arm shall be fixed to the base of the ala nares, with the head in the position of 30° flexion and 45° extension. Then, in addition to normal clinical procedures, these two head positions will take right and left direct digital interocclusal records. These records will take one minute for each main position, and inter-occlusal records will be completed in a total of three minutes. The closing movement will be repeated to get the participants to an intercuspal jaw position, and the muscles will get used to this position. Subsequently, participants will be asked to close their mandible in a repeated intercuspal position and they will be asked to maintain this position. The intraoral scanner will be placed between the teeth and the cheek with minimum pressure, without disturbing the closure, and will be recorded from the teeth's buccal surfaces with movement from the rear to the front. The TRIOS software will automatically match the same areas in the dental arch scans during the interocclusal record with the scan of the buccal surface of the teeth, closing the scans of the lower and upper jaws. Participants will repeat the same procedure for right and left interocclusal records without disturbing the intercuspal jaw position. The oJMA will be recorded at the second session and last 15 minutes. All recordings will then be integrated into the analytical module of the oJMA software (zebris WINJAW+; zebris Medical GmbH, Germany) in 'stl' format.

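### The order of the three head-position records is neither randomised nor stated; if all volunteers follow one order, drift or carry-over cannot be told apart from posture

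*Combined protocol and SAP*

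**What the plan says.** The Randomization section says the recordings "will be completed in a single session, and the recording groups will not change", and then: "The total of three different records to be taken will not be subject to randomization in itself".

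The order has to be pieced together from other sections:

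- Digital Interocclusal Record Groups lists neutral as G1 ("Digital interocclusal recording taken in the neutral position with the head aligned in the head-neck-spine plane"), then flexion as G2 and extension as G3.
- oJMA Record says "For each participant, the neutral position will first be determined". This concerns finding the position with the goniometer, not taking the record.
- The same section continues: "Then, in addition to normal clinical procedures, these two head positions will take right and left direct digital interocclusal records". Flexion and extension are named together and never ordered relative to each other.

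The oJMA Record section allots one minute per position and three minutes in total, with no interval between records. It also describes rehearsal of closure: "The closing movement will be repeated to get the participants to an intercuspal jaw position, and the muscles will get used to this position". It does not say whether this is repeated before each position. On staffing it says "All records will be completed in two sessions and carried out by a single operator". The Blinding section says there is no blinding.

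The Primary Conclusion Point is the difference in contacts between head positions. Statistical Evaluation names candidate tests but no term for order or record number.

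**The concern.** Every volunteer supplies all three records, so there is no need to randomise volunteers to groups. The order of the records is the part of this design that needs protection. If all volunteers follow one order, anything that changes from the first record to the third is read as a posture effect or hides a real one. The same is true of anything left over from the preceding position.

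The protocol itself names mechanisms by which this could happen. Importance of the study says: "Any change in head posture causes the muscles attached to the mandible to stretch and lengthen, resulting in a change in mandibular position". The recording procedure relies on the muscles adapting through repeated closure. Neither statement shows that an effect persists or accumulates, but the plan has no means of ruling it out.

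**Working it through.** **Inputs.** From the documents: n = 36 (Enrollment), repeat correlation r = 0.20 and alpha 0.05 (Sample size and strength analysis), three records per volunteer. Assumed: a two-sided test, the size t of a linear drift per record, the size c of a carry-over from the preceding position, and r = 0.50 and 0.80 as alternatives. Drift and carry-over are in SD of a single record, because the outcome metric is not defined. The plan gives no figure on order effects, so there is none to reproduce.

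**1. Can order and position be separated?** Take a linear model with volunteer (36 columns), position (2) and record number (2), 40 columns in all. Under one common order its rank is 38, so the two record-number columns duplicate the two position columns. Under six balanced orders with 6 volunteers each the rank is 40. The variance of a pairwise position contrast is 2/36 = 0.0556 of the within-volunteer variance, with or without record number in the model.

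**2. Common order, linear drift, no true effect.** The third-minus-first difference is biased by 2t. Its SD is sqrt(2(1 - r)), so the paired test has noncentrality 2t x sqrt(36) / sqrt(2(1 - r)) on 35 df. The repeated-measures F has noncentrality 36 x 2t^2 / (1 - r) on 2 and 70 df.

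Example, t = 0.10 and r = 0.20: the SD is sqrt(1.6) = 1.265. Paired noncentrality is 0.20 x 6 / 1.265 = 0.949, which gives 15.2%. F noncentrality is 36 x 0.02 / 0.8 = 0.90, which gives 12.1%.

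| Drift per record | Bias, 3rd - 1st | Paired, r=0.20 | Paired, r=0.50 | Paired, r=0.80 | RM F, r=0.20 |
|---|---|---|---|---|---|
| 0.05 | 0.10 | 7.5% | 9.0% | 15.2% | 6.7% |
| 0.10 | 0.20 | 15.2% | 21.5% | 45.4% | 12.1% |
| 0.125 | 0.25 | 21.1% | 30.8% | 63.5% | 16.4% |
| 0.25 | 0.50 | 63.5% | 83.1% | 99.6% | 53.6% |

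The paired rate reaches 10% at a drift of 0.071, 0.056 or 0.035 SD per record for r = 0.20, 0.50 or 0.80.

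Other tests were simulated at r = 0.20 with 20,000 trials per scenario, for the same four drifts:

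- Friedman: 6.6, 10.5, 14.1 and 42.1%.
- Kruskal-Wallis: 3.5, 6.7, 9.8 and 39.9%.
- One-way ANOVA: 3.6, 7.1, 10.3 and 42.4%.

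The last two look milder only because they ignore the pairing; with no drift they reject in 2.4% and 2.5%. The bias is the same whichever test is used.

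**3. Masking.** With a true third-minus-first effect of 0.50 SD and r = 0.20, the paired test has 63.5% power. An opposite drift of 0.10 SD per record leaves 0.50 - 0.20 = 0.30 SD and 28% power. A drift of 0.25 SD per record leaves nothing.

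**4. Six balanced orders, same drifts.** The extension-minus-neutral bias is zero. The paired rejection rate is 4.2-4.9% at r = 0.20 and 2.5-4.9% at r = 0.80. With a record-number term (108 - 40 = 68 residual df) it is about 5% at both.

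**5. Carry-over, c = 0.50, r = 0.20.** In the order neutral-flexion-extension, carry-over from flexion biases extension-minus-neutral by +0.50 SD (63.5% false positives). It leaves flexion-minus-neutral unbiased, and carry-over from extension affects neither contrast.

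In balanced orders, extension directly precedes neutral in 2 of 6, so its carry-over biases extension-minus-neutral by -c/3 = -0.17 SD (about 11%). By symmetry, carry-over from flexion biases flexion-minus-neutral by the same amount. Carry-over from flexion no longer biases extension-minus-neutral. A record-number term does not help here (11.0% against 11.1%).

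**The case against.** **The common order is inferred.** The group list is a set of definitions, and determining neutral first concerns the goniometer axis. The statement that the groups stay the same may mean only that every volunteer supplies all three records. This is right, and the conclusion is therefore conditional. If the order varied at the operator's discretion, confounding would be partial, but order would be uncontrolled, and nothing says it would be noted.

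**No order effect is shown.** The muscle-stretch statement does not say that the effect outlasts the posture, and closure rehearsal reads naturally as a stabilising step. One-minute records, a single operator and the exclusion of jaw-joint and neck problems may keep drift small. This also stands. At 0.05 SD per record and r = 0.20 the error rates are close to nominal. The largest rates need a total drift of 0.50 SD. That equals the plan's own 0.50 only if both are on the same scale, which cannot be confirmed because the symbol is lost in the text.

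**Balancing has a price.** A neutral-first order protects the neutral record from carry-over. Balanced orders expose it, so both contrasts against neutral can pick up a bias of -c/3. This is correct and must be weighed. It does not overturn the remedy, because balancing removes the drift bias altogether and also removes the larger +c bias in extension-minus-neutral.

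**Conclusion.** The concern holds. The records are expressly not randomised, no order is stated, and nothing in the design or analysis would detect or adjust for an order effect. If one order is used throughout, position and record number cannot be separated by any test or any increase in sample size.

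Whether this would distort the result is unknown. The error rates rest on assumed drift and carry-over sizes and on an undefined outcome metric, so they show sensitivity and are not a forecast. The point should be fixed because the remedy is cheap and is available only before data are collected. Confidence is medium, since the common order is inferred.

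**What to change.** Replace the last sentence of the Randomization section with: *The order of the three head-position records is randomised for each volunteer, balanced over the six possible orders, and noted on the case report form.* In addition:

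- Keep setting the goniometer reference axis in neutral first; only the order of recording changes.
- If a parametric within-person model is used, include record number (1, 2, 3) as a fixed effect.
- Give a replacement volunteer the order of the volunteer replaced, to keep the balance.
- State whether closure rehearsal is repeated before each record, since balancing alone does not remove carry-over.

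If the sponsor keeps a fixed order, state it, justify it and list order effects as a limitation on attributing differences to posture. A repeat neutral record at the end would then allow a check for drift.

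**Cost.** Randomising needs an allocation list, some extra repositioning and 2 degrees of freedom (68 residual df instead of 70). It needs no extra volunteers, visits or records. Planned times are 3 + 3 + 15 = 21 minutes against the 25-minute limit in Enrollment, so repositioning has to fit in about 4 minutes. The statistical price is the exposure of some neutral records to carry-over, a bias of -c/3 in the contrast between neutral and the position carried over.
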